3.7 Adverse Events

3.7.1 Recording Adverse Events

If adverse events (AEs) occur, the first concern will be the welfare of the subject, including any treatment the Investigator believes is appropriate.

Adverse events that occur during the trial whether they are device related or not, will be documented. An adverse event is defined as any **clinically significant** new or changed untoward condition, or a condition requiring treatment, either surgical or medical intervention.

- Recording of all AEs shall include the AE term and assessed relationship of the event to the study device/procedure. Additionally:
 - a. Recording of ocular AEs and related AEs shall include the start and resolution dates, severity, and treatment (if any).
 - b. Recording of non-ocular AEs that are not related to the study treatment will be limited to documenting the start and resolution dates (if any) from subject self- reports or other avenues and no additional information will be recorded.
 - c. All AEs will be documented on the AE CRF.
- 2. Postoperative inflammation within or at 30 days post-surgery will be reported as an AE for cells and flare graded as 3+ or 4+.
- 3. Ocular events occurring greater than 30 days postoperatively that meet the following criteria will be reported as AEs.
 - a. For evaluations for which a standard grading scale is available, ocular AEs will be captured for significant (2-grade) worsening.
 - b. For evaluations where a standard grading scale is not available, clinically significant events assessed as mild, moderate, or severe will be captured as AEs.
- 4. For related, systemic AEs or all ophthalmic AEs treated with surgical intervention, the intervention should be recorded in the Ocular Procedure Log as a treatment for the AE, and the interventional treatment will not be recorded as a separate AE. If a single condition results in multiple protocol defined AE's, the root cause AE will be recorded, and the other events will be recorded as sequelae. (For example, an increase in crystalline lens opacity of greater than 3 half step increments that leads to a VF Mean Deviation loss of greater than 2.5dB. The crystalline lens opacity is recorded as an AE, and the VF Mean Deviation loss is recorded as a sequela).
- 5. The severity (intensity) of AEs will be rated as follows:
 - a. **Mild:** subject has no, transient, or mild discomfort (< 48 hours); signs and symptoms are transient; symptoms do not interfere with the subject's daily activities; symptoms do not require medication or a medical evaluation.
 - b. **Moderate:** subject has moderate discomfort; signs and symptoms are persistent; subject has some limitation in activity, or some assistance may be needed; symptoms may require no treatment or minimal medical intervention/therapy.
 - c. **Severe:** subject has marked limitation in activity; signs and symptoms are persistent; symptoms interrupt participant's usual daily activity and may require medical intervention/therapy or surgery.

- 6. Adverse Events will be assessed by the PI for relatedness to the device / procedure. The relatedness will be determined to be:
 - a. **Definitely Unrelated**: The cause of the AE is in no way related to any aspect of the study procedure, device, or study testing.
 - b. **Unlikely Related:** The adverse event is unlikely to be related to the study procedure, device, or study testing, and other more likely causes are present. Relatedness cannot be ruled out with certainty.
 - c. Possibly Related: An AE is possibly related when there is a reasonable possibility that the event might have been caused by the study procedure, device, or study testing. A possibly related event may follow no known pattern of response and an alternative cause seems more likely. In other circumstances there may be significant uncertainty about the cause of the event, or a possible relationship to study participation cannot reasonably be ruled out.
 - d. **Probably Related:** An AE is probably related when there is a reasonable possibility that the event is likely to have been caused by the study procedure, device, or study testing. The AE has a timely relationship to the study procedure(s) and follows a known pattern of response, but a potential alternative cause may be present.
 - e. **Definitely Related:** An AE is definitely related to study participation if the event was caused by the study procedure, device, or study testing. A definitely related event has a strong temporal relationship and an alternative cause is unlikely.

Throughout the course of the study, all efforts will be made to remain alert to possible adverse experiences or untoward findings.

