1.1.3 Study Summary

Study Summary						
Study Objective	The purpose of study is to obtain initial evidence of the safety of image guided, femtosecond laser glaucoma surgery using the ViaLase Laser for the treatment of primary open angle glaucoma.					
Study Population	Subjects at least 45 years of age, of either sex, and any race or ethnicity, with refractory Primary Open Angle Glaucoma (POAG) with IOP between 21 and 35 mmHg using 1 or more IOP lowering medications.					
Safety Outcomes	Immediate safety outcomes will be assessed during the Operative day (day-0), 1-day and 1-week visits:					
	 Percentage patients with elevated IOP equal or greater than 6 mmHg at 1-hour post-treatment 					
	Percentage of patients with iritis, anterior chamber flare and cells					
	Percentage of patients with Hyphema					
	Percentage of patients with corneal haze					
	Additional, longer-termed, safety outcomes will be assessed by monitoring clinical data including:					
	 Changes in best spectacle corrected visual acuity (BSCVA) 					
	Peripheral anterior synechiae (PAS)					
	Cornea endothelial cell count					
	Endothelial cell count					
	Slit lamp findings					
	Corneal thickness (pachymetry)					
	Visual field					
	Fundus findings					
	Other gonioscopic findings additional to PAS					
	The number of glaucoma medications used					
	Adverse events					
	Procedure-related complications					

Study Summary						
Adverse Events	All adverse events will be summarized, tabulated, and analyzed by: Seriousness Severity Outcome Relationship to the study device Relationship to the study procedure.					
Examination Schedule	The examination schedule for study subjects will be as follows: Subject Eligibility Preoperative Evaluation Operative Evaluation Postoperative Day 1 Postoperative Week 1 Postoperative Month 1 Range 5 - 9 days post-op Postoperative Month 3 Range 70 – 105 days post-op Postoperative Month 6 Range 168 – 196 days post-op Postoperative Month 12 Range 330 – 420 days post-op					

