1.5.3 Adverse Events

All adverse events will be summarized, tabulated, and analyzed by:

- Seriousness
- Severity
- Outcome
- Relationship to the study device
- Relationship to the study procedure.

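### Severity is never recorded for non-serious, unrelated, non-ocular AEs (3.7.1 item 1b), although 1.1.3 and 1.5.3 promise to tabulate all AEs by severity and outcome

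*Combined protocol and SAP*

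**What the plan says.** The analysis promise appears twice without exception. The synopsis (1.1.3) reads: "All adverse events will be summarized, tabulated, and analyzed by: Seriousness Severity Outcome Relationship to the study device Relationship to the study procedure". Section 1.5.3 repeats it with the same five classifications.

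The recording rules are in 3.7.1:

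- Item 1, lead-in, for every event: "Recording of all AEs shall include the AE term and assessed relationship of the event to the study device/procedure".
- Item 1a: "Recording of ocular AEs and related AEs shall include the start and resolution dates, severity, and treatment (if any").
- Item 1b, for non-ocular events not related to treatment: recording "will be limited to documenting the start and resolution dates", and "no additional information will be recorded".
- Item 1c puts every AE on the AE CRF.
- Item 5, with no exception for any class of event: "The severity (intensity) of AEs will be rated as follows".
- Item 6 has the PI assign one of five levels of relatedness.

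Three other sections bear on the point. Section 3.7.3 requires an AE form and SAE report forms for all serious events, related or not. Section 3.7.5 requires follow-up to a documented outcome for ophthalmic AEs and related systemic AEs. Section 3.9 commits to the number and percentage of patients with any AE; seriousness, severity and relationship are to be listed as appropriate where collected. It does not mention outcome.

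**The concern.** A table can show only what the CRF collects. Item 1a names severity and item 1b excludes it, so the exclusion looks deliberate. It contradicts the tabulation promised in 1.1.3 and 1.5.3, and also item 5 of the same section.

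Safety is the study's sole stated objective. The trial has one arm and at most 20 subjects, so one subject is at least 1/20 = 5% of any percentage reported. How much is recorded about a systemic event depends on the PI's relatedness judgement, made with no control arm to inform it. If that judgement is later revised, no severity rating will have been made at the time of the event.

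The boundary is also unclear. Item 1b applies to events that are not related, but item 6 has five levels, and its definition of Unlikely Related says that a relationship cannot be excluded with certainty. Section 3.7.5 counts that level among those of potential relatedness. Two members of site staff could record the same event under different rules.

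**Working it through.** The plan gives no figure to reproduce, so the check sets each promised classification against the fields that the recording rules supply.

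| Classification promised in 1.1.3 and 1.5.3 | Ocular or related AEs | Unrelated non-ocular AEs, non-serious | Unrelated non-ocular AEs, serious |
|---|---|---|---|
| Relationship | Recorded (item 1 lead-in) | Recorded (item 1 lead-in) | Recorded (item 1 lead-in) |
| Seriousness | Not named in 1a; derivable from SAE forms (3.7.3) | Derivable: no SAE form implies non-serious | Derivable from SAE forms (3.7.3) |
| Severity | Recorded (item 1a) | Barred by 1b, although item 5 implies a rating | AE form required by 3.7.3, but 1b pulls the other way |
| Outcome | Not named in 1a; followed and documented under 3.7.5 | Only resolved or not, from the resolution date | 3.7.3 asks for the outcome to be reported to the sponsor |

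1. **Relationship** can be tabulated for all events.
2. **Seriousness** can be tabulated for all events. It needs no field under item 1b, because 3.7.3 applies whatever the site or relatedness of the event.
3. **Severity** fails for the non-serious events in the third column. Item 1b closes with "no additional information will be recorded", so a site that follows it leaves the rating blank. Item 5 points the other way, and nothing says which item prevails.
4. **Outcome** is partial for the same events. A resolution date separates resolved from unresolved, but not resolution with sequelae, which 3.7.5 treats as a category of its own. Section 3.7.5 does not extend its follow-up duty to unrelated systemic events.
5. **Section 3.9** can be carried out under item 1b, because it lists only what was collected. The conflict is therefore with 1.1.3 and 1.5.3. Section 3.9 is in effect a third and weaker description of the AE analysis.

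The affected cells are thus severity (no source) and outcome (partial) for AEs that are at once non-ocular, judged not related, and non-serious.

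**The case against.** The strongest reply is that this is overview wording running ahead of a sensible recording rule. The statistical section, 3.9, promises less and can be delivered in full. Limiting detail on unrelated systemic events is the sponsor's choice, and the ocular events at the heart of the study keep their severity rating whatever their relatedness. That limits the size of the point. It does not remove the conflict, because 1.1.3 and 1.5.3 say all events, and item 5 conflicts with item 1b within 3.7.1 itself.

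A reader might infer more than the documents support:

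- *That these events are recorded with dates alone.* They are not: the lead-in to item 1 requires the term and assessed relationship, and the dates come in addition.
- *That seriousness is lost.* It is not: the SAE forms are mandatory for every serious event.
- *That no overall AE table can be produced.* Counts, relationship and seriousness can all be tabulated.
- *That a complaint recurring across subjects would go unseen.* Terms and dates are kept for every event, so recurrence stays visible; only its severity does not. An event around the procedure would normally be rated at least possibly related and so fall under item 1a.
- *That severity could never be recovered after reclassification.* An event reclassified as related comes under item 1a, and 3.7.3 lets the sponsor request records depending on the nature and seriousness of the event. A retrospective rating is weaker than one made at the time, but it is not shown to be impossible.

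The class may also be narrow. If 3.7.5 governs, Unlikely Related falls outside item 1b, leaving only events rated definitely unrelated. Item 1b does not say so.

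**Conclusion.** The point holds in limited form. A stated safety tabulation cannot be completed under an explicit recording limit: for non-serious, non-ocular AEs judged not related, severity is never captured and outcome is known only as resolved or not. Within that class the severity gap is complete. Outside it, the severity tables for ocular and related AEs are intact.

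How many events are affected cannot be worked out from the documents. They give no expected AE rate, and an AE must be clinically significant or need treatment to count. The conclusion assumes that sites follow item 1b as written. The AE CRF is not among the documents, so it may already hold a severity field; if it does, the form and item 1b disagree and still need to be reconciled.

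This is a minor point. It does not threaten the main ocular safety results, but it is worth correcting in a small trial whose only objective is safety.

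**What to change.** Preferred: replace the whole of item 1b's limit. Removing only the closing clause would leave the opening restriction to dates in force. The new rule would say that, for every AE, the CRF required by item 1c records term, start and resolution dates, seriousness, severity, outcome and assessed relationship, with treatment added for ocular and related AEs. This also names seriousness and outcome for ocular and related events, which item 1a does not do. The cost is three fields on a form already completed for each AE, and a little site time.

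If the sponsor keeps the limit: restrict the severity and outcome tabulation in 1.1.3 and 1.5.3 to ocular AEs, related AEs and all SAEs, and list the remaining AEs by term, dates and relationship. All SAEs must be named, or unrelated non-ocular serious events, deaths included, would drop out of the tables. Limit item 5 to the same set, and state in item 1b that it does not apply to serious events. This costs a few sentences, and severity stays unknown for the remaining events.

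In either case, state whether Unlikely Related falls under item 1a or 1b, consistently with 3.7.5, and bring 3.9 into line with 1.1.3 and 1.5.3, including outcome.

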3.7.2 Adverse events knowing to occur during or after laser procedures

Specific examples of adverse events that potentially may occur during or after laser surgery (regardless of likelihood) include but are not limited to:

- Choroidal hemorrhage
- Choroidal effusion
- Cyclodialysis cleft
- Significant hyphema (i.e. ≥ 10% of anterior chamber)
- Significant iris damage

Possible postoperative adverse events:

- Allergic reaction
- Intraocular inflammation (not pre-existing) remaining or arising after the protocol's specified medication regimen is complete
- Choroidal effusion
- Choroidal hemorrhage
- Aqueous misdirection
- Chronic pain in the study eye present greater than 3 months postoperative
- Clinically significant cystoid macular edema

- Corneal abrasion
- Flat or shallow anterior chamber (e.g., shallowing of the anterior chamber that causes any amount of iris-cornea touch)
- Hypotony (IOP < 6 mmHg) associated with clinically significant findings. (Clinically significant hypotony is defined as hypotony maculopathy or hypotony with flat anterior chamber requiring reformation, corneal folds, choroidal effusions requiring drainage, and/or suprachoroidal hemorrhage)
- Increase in C/D ratio of > 0.3 units
- IOP increase requiring management with oral or intravenous medications or with surgical intervention
- IOP increase ≥ 10 mmHg vs. baseline IOP occurring at any visit
- Iridodialysis
- Loss of best spectacle corrected visual acuity (BSCVA) of 2 lines or more (logMAR scale; 10 letters or more on ETDRS chart)
- Pupillary block
- Secondary surgical intervention
- Significant corneal complications including opacification and decompensation
- Significant corneal edema (NOTE: A classification of mild to moderate corneal edema up to and including the Week 1 postoperative exam is NOT considered an adverse event)
- Significant hyphema (≥ 10% of anterior chamber)
- Vitreous hemorrhage
- Worsening in visual field of mean deviation (MD) of ≥ 2.5 dB compared to the MD used to determine subject eligibility (confirmed in at least 2 out of 3 postoperative visual field tests performed within a 90-day period)

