3.9 Statistical Methods

Descriptive statistics will be used for reporting available study results. Baseline and demographic characteristics will be presented. Continuous variables will be summarized by descriptive statistics such as mean, standard deviation, median, minimum, and maximum. Discrete variables will be summarized by frequency tables and percentages.

Adverse events will be summarized by presenting the number and percentage of patients experiencing any adverse event. Any other information collected such as seriousness, severity, and relationship to study device and procedure will be listed as appropriate.

IOP change from baseline will be summarized at each evaluation by mean, standard deviation, and range. Changes in IOP from baseline (Day 0 prior to assigned treatment) will be summarized at each visit. The proportion of subjects with an IOP reduction of 20% or more from baseline will be tallied at each post-operative visit. The number and frequency of medications will be tallied at each visit.

Slit lamp exam and fundus exam findings will be summarized at each visit using frequency and percentage.

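### The recording rule in 3.7.1 item 4 conflicts with the adverse event list in 3.7.2, so counts by event type can understate vision loss, pressure rise, field loss and, most clearly, re-operation

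*Combined protocol and SAP*

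**What the plan says.** Section 3.7.2 gives examples of possible postoperative adverse events. They include "Loss of best spectacle corrected visual acuity (BSCVA) of 2 lines or more", "IOP increase ≥ 10 mmHg vs. baseline IOP occurring at any visit", a confirmed visual field mean deviation worsening of at least 2.5 dB, and, without any qualifier, "Secondary surgical intervention".

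Section 3.7.1 item 4 sets two recording rules that bear on the same events:

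- Surgery used to treat an ophthalmic adverse event (or a related systemic one) is entered in the Ocular Procedure Log, and "the interventional treatment will not be recorded as a separate AE".
- Where one condition leads to several protocol-defined events, "the root cause AE will be recorded, and the other events will be recorded as sequelae". The worked example is explicit: "The crystalline lens opacity is recorded as an AE, and the VF Mean Deviation loss is recorded as a sequela".

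Section 3.7.1 item 1 requires the term and the assessed relationship for every adverse event, plus dates, severity and treatment for ocular and related ones. It states no such requirement for sequelae.

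On reporting, 1.5.3 promises tables of all adverse events by seriousness, severity, outcome and relationship to device and procedure. Section 3.9 specifies "presenting the number and percentage of patients experiencing any adverse event", with other attributes listed as appropriate. Neither section mentions sequelae or the Ocular Procedure Log.

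**The concern.** Initial evidence of safety is the only objective stated in 1.3. The same event is an adverse event under 3.7.2 and not one under item 4, depending on whether the investigator names a cause for it. A table built from adverse event records would then show the mechanism (for example hyphema or lens opacity) without the consequence for pressure, field, acuity or further surgery. The consequence would also have no required severity, dates or relationship of its own, and so no place in the 1.5.3 tables.

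Re-operation is most exposed. Section 3.7.5 foresees that a subject may need additional glaucoma surgery. If that surgery treats an ophthalmic adverse event, item 4 sends it to a log that no planned summary draws on.

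**Working it through.** The plan gives no sample-size, power or error-rate figure on this point, so there is nothing to reproduce. The check compares the rules and then counts an assumed example both ways.

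**Step 1: when item 4 removes an event from the adverse event records.**

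| 3.7.2 event | Stands alone | Attributed to another adverse event | Other planned summary |
|---|---|---|---|
| Acuity loss of 2 lines or more | Adverse event | Sequela only | Acuity change is a long-term outcome (1.5.2); 3.9 names no count at this threshold |
| Pressure rise of 10 mmHg or more | Adverse event | Sequela only | Pressure change by visit: mean, SD and range (3.9); rise of 6 mmHg or more at 1 hour (1.5.1) |
| Field worsening of 2.5 dB or more | Adverse event | Sequela only | Visual field is a long-term outcome (1.5.2); 3.9 names no count at this threshold |
| Secondary surgery | Adverse event if it treats no recorded adverse event | Procedure log only, if it treats an ophthalmic or related systemic adverse event | None in 3.9; 1.5.2 names procedure-related complications without defining them |

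**Step 2: an assumed example, not trial data.** Take n = 20 treated, one eye each (1.4 allows up to 20 consented subjects). Subject A has hyphema that qualifies as an adverse event and leads to a pressure rise of 10 mmHg or more. Subject B has lens opacity leading to field loss, acuity loss and surgery. Subject C has isolated acuity loss.

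| Count | Under item 4 | Every event counted |
|---|---|---|
| Hyphema | 1/20 | 1/20 |
| Lens opacity | 1/20 | 1/20 |
| Pressure rise | 0/20 | 1/20 |
| Field loss | 0/20 | 1/20 |
| Acuity loss | 1/20 | 2/20 |
| Secondary surgery | 0/20 | 1/20 |
| Total event lines | 3 | 7 |
| Subjects with any adverse event | 3/20 = 15% | 3/20 = 15% |

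The last row is the same both ways because the root-cause event keeps each subject in the numerator.

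**Step 3: size per eye.** Each recoded eye lowers its own event-type rate by 100/n percentage points: 100/20 = 5 points at n = 20, and more if fewer are treated.

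Exact (Clopper-Pearson) 95% limits are the 2.5% quantile of Beta(x, n − x + 1) and the 97.5% quantile of Beta(x + 1, n − x); for x = 0 the lower limit is 0. At n = 20:

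- 0/20 = 0% (0 to 16.8%)
- 1/20 = 5% (0.1 to 24.9%)
- 2/20 = 10% (1.2 to 31.7%)

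The plan is descriptive and does not call for these intervals. They show only how little separates the counts statistically. What changes is whether the table reports that the event occurred.

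**The case against.** The strongest reply is that little is lost. The one adverse event count that 3.9 specifies does not move. Sequelae are still recorded, surgery is still logged, and treatment is a required field for each ocular adverse event. Tables by outcome are promised, and 3.7.5 recognises resolution with sequelae as an endpoint. Acuity, field and procedure-related complications are outcomes in their own right. With about 20 eyes, a large pressure rise at a summarised visit would show in the range. Section 3.7.2 is a list of examples, so the two sections can be read together: surgery is an adverse event unless it treats one. The case report form is not in the documents and may already link events.

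Most of this stands, and it rules out some stronger readings:

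- A reader might infer that these events vanish from safety reporting. They do not: item 4 applies only to events attributed to another adverse event, or to surgery that treats one, and the measurements remain in the data.
- A reader might picture several pressure spikes, all caused by hyphema, tabulated as none. That is an assumed extreme. It also needs each hyphema to qualify as an adverse event; the 3.7.2 entry is for at least 10% of the anterior chamber.
- A reader might object that vision loss following an unrelated root cause leaves the related counts. That alone is not a flaw, since a consequence of an unrelated event is itself unrelated.

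What the reply does not answer is that no section commits to counting eyes that meet each 3.7.2 criterion, or to counting secondary surgeries. A range shows the worst eye, not how many eyes crossed a threshold. An outcome coded as resolved with sequelae need not say which sequela. Reading the two sections together still leaves re-operation for an ophthalmic adverse event without a planned count.

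**Conclusion.** The conflict is real, and its effect is limited. When an acuity, pressure or field event from 3.7.2 is attributed to another adverse event it is recorded only as a sequela, and surgery treating an ophthalmic adverse event is recorded only as treatment. Counts by event type, and the 1.5.3 tables by severity, outcome and relationship, can therefore be too low by 5 points per eye if 20 are treated. Stand-alone events and the any-event percentage are unaffected. Re-operation is the clearest gap because 3.9 has no other summary of it.

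This rests on two assumptions: that the tables will be built from adverse event records as item 4 defines them, and that no unpublished form or table plan adds the sequelae back. How many events would be recoded cannot be known from the documents. In a study whose only objective is safety this should be fixed, but it does not block the study.

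**What to change.** 1. Reconcile 3.7.1 item 4 with 3.7.2, stating how secondary surgery is classified when it treats an adverse event. Align the field-loss wording too: the item 4 example uses more than 2.5 dB, while 3.7.2 uses 2.5 dB or more.
2. Keep the root-cause link, but record severity, dates and relationship for each 3.7.2 event coded as a sequela.
3. In 3.9, tabulate the number and percentage of eyes meeting each 3.7.2 criterion, whether coded as adverse event, sequela or treatment. Place this beside a root-cause table so that readers can see the overlap.
4. In 3.9, report the number and percentage of eyes with any secondary ocular surgery, taken from the Ocular Procedure Log.

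The cost is a reworded paragraph, a few more form entries and one extra table. The measurements and the log already exist; the attributes of sequelae may be new data collection, since the plan does not state that they are captured. Event counts will look slightly less favourable. No clinical rule changes.

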3.7.4 Unanticipated Adverse Device Effect

Unanticipated adverse device effect (UADE) is defined as any serious adverse effect on health or safety or any life-threatening problem or death caused by, or associated with, a device, if that effect, problem, or death was not previously identified in nature, severity, or degree of incidence in the investigational plan or application (including a supplementary plan or application), or any other unanticipated serious problem associated with a device that relates to the rights, safety, or welfare of subjects. Date and time of the event, its severity, treatment if any, and the assessed relationship of the event to the study device will be recorded on the AE form.

Unanticipated adverse device effects must be reported to ViaLase and to the Investigator's IRB as soon as possible, but in no event later than 10 working days after the Investigator first learns of the event. Subjects who are exited from the study due to unanticipated adverse device effects will be followed until their medical outcome is determined; the Investigator must provide written reports to the ViaLase Study Manager.

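### AE tables are promised separately by relationship to the device and to the procedure, but the relatedness rating the protocol specifies pools device, procedure and study testing, so it cannot supply them

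*Combined protocol and SAP*

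**What the plan says.** On reporting, section 1.5.3 opens with "All adverse events will be summarized, tabulated, and analyzed by" and lists five factors. Relationship to the device is one bullet and "Relationship to the study procedure" is another. The synopsis (section 1.1.3) has the same two entries: "Relationship to the study device Relationship to the study procedure". Section 3.9 also names both relationships, but says only that they will be listed where appropriate.

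On recording, section 3.7.1, item 1, asks for one relationship per AE, to device/procedure. Item 6 says how it is judged: "Adverse Events will be assessed by the PI for relatedness to the device / procedure". One five-level scale follows. Its top level reads: "An AE is definitely related to study participation if the event was caused by the study procedure, device, or study testing". The other four levels name the same three sources together.

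Section 3.7.4, on unanticipated adverse device effects, says that "the assessed relationship of the event to the study device will be recorded on the AE form". No definition of a device-only relationship accompanies it.

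**The concern.** The study's one stated objective is initial evidence on the safety of the laser. It has a single arm, so no control group shows how often the examinations alone cause harm. The investigator's attribution is then the main means of separating device harm from other harm. If that attribution pools three sources, the two promised tables cannot differ on the stated rule, and harm from an examination can be read as harm from the laser. Section 3.7.4 is affected too, because deciding whether an event is a device effect needs a judgement about the device alone.

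**Working it through.** The plan states no figure on this point, so the check sets what is promised beside what is collected.

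| Section | Relationship to device | Relationship to procedure | Relationship to study testing |
|---|---|---|---|
| 1.1.3 and 1.5.3 (reporting) | separate factor | separate factor | not mentioned |
| 3.9 (statistical methods) | named, to be listed | named, to be listed | not mentioned |
| 3.7.1 item 1 (recording) | joint with procedure | joint with device | not mentioned |
| 3.7.1 item 6, all five levels | pooled | pooled | pooled |
| 3.7.4 (unanticipated device effects only) | recorded | not mentioned | not mentioned |

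**Test of the rule.** Take three events, each with close timing and no plausible alternative cause:

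1. tissue damage from the laser beam;
2. an injury from another part of the operative procedure;
3. a corneal abrasion from a tonometer or gonioscopy lens at a follow-up visit. Corneal abrasion is on the protocol's own list of possible postoperative events in section 3.7.2.

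Under item 6 all three are Definitely Related. The scale maps three causes to one code, and no section gives a rule for splitting that code afterwards. The rating yields one pooled rate, not a device rate and a procedure rate.

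**Does another section supply the split?** Section 3.7.4 does so only for serious, unanticipated device effects, a subset of AEs. Section 3.9 assumes that both relationships have been collected but does not define either.

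**Effect of one testing-caused event coded as related.** Section 3.9 counts patients, and sections 1.1.2 and 1.4 cap consent at 20.

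- Patient has no other related AE: shift = 1/n, with n ≤ 20, so at least 1/20 = 5 percentage points.
- Patient already has a related AE: shift = 0.
- If events rather than patients were counted, one event among M AEs is a share of 1/M, which is below 5 points whenever M exceeds 20.

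**The case against.** The strongest reply concerns the form. The AE form is not in the public documents, and the slash in device / procedure could mean either or both. Sections 3.7.4 and 3.9 both suggest that a device item may exist on the form. That stands as a limit: the protocol's wording points to one rating, but the form may hold two. It does not remove the problem, because two fields completed from the item 6 definitions would each still ask about all three sources.

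It is also fair to say that little depends on the rating. Section 3.9 promises only a listing of relatedness, no endpoint or stopping rule uses it, and up to 20 patients can be read case by case. Pooling also errs towards attributing harm to the study. This limits the damage. But section 1.5.3 still promises tables, and a case-by-case reading would have to work from the same pooled code.

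Three stronger readings are tempting, and the documents do not support them.

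- *Every testing-caused AE adds at least 5 points.* It does so only for a patient with no other related AE.
- *The risk from testing is large.* Appendix A has 6 single and 2 × 3 = 6 diurnal postoperative pressure timepoints. That is 12, or 11 if the Month 3 single reading is one of the diurnal ones. At two readings each (B.5), this gives 22 to 24 applanations, plus 5 gonioscopies. These counts show exposure. No AE probability per contact is given, and section 3.7.1 counts only clinically significant conditions or those needing treatment.
- *The split between Unlikely and Possibly Related is arbitrary.* The first level includes "and other more likely causes are present" and the second allows that "an alternative cause seems more likely". The wording is untidy, but the leading tests differ: one requires that a relation be unlikely, the other that it be a reasonable possibility. Deleting the second clause would move events down to Unlikely, which is the anti-conservative direction in a safety study.

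**Conclusion.** The point holds as a mismatch between what is promised and what is specified. Device-related and procedure-related AE rates cannot be derived from the rating in section 3.7.1, and testing-caused events are not distinguishable from laser injury. The conclusion rests on the protocol text alone. It assumes that investigators apply the item 6 definitions as written, whatever the layout of the form.

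The size of any distortion is unknown, since it depends on how many AEs are caused by testing and in which patients. It could be nil. It is nevertheless worth correcting in a single-arm study of device safety, and before events are rated, because a later split would mean adjudicating every AE again.

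**What to change.** In section 3.7.1, items 1 and 6, and on the AE form, rate every AE separately for relationship to the ViaLase Laser, to the operative procedure and to study testing. Keep the same five levels, but word each definition for one source at a time, including the top level, which now refers to study participation as a whole. Leave the clauses that separate Unlikely from Possibly Related as they are.

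Then tabulate device and procedure relationship separately, as section 1.5.3 states. Change section 3.9 from listing to the same tabulation, and use the device rating for section 3.7.4. Section 3.7.5 can keep its present scope if an event counts as potentially related whenever any of the three ratings is above Definitely Unrelated.

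The cost is protocol wording and slightly more data entry per AE by the same investigator. Treatment, visits and sample size do not change. One limitation remains: laser and procedure take place in the same session, so attribution between them will sometimes be uncertain, and the ratings should be allowed to show that.
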